**Investigation of the Effectiveness of Visual Feedback
Training on Upper Extremity Functions in Cerebral Palsy**

**Study Protocol with Statistical Analysis Plan (SAP) and
Informed Consent Form (ICF)**

January 1, 2018

**Investigation of the Effectiveness of Visual Feedback
Training on Upper Extremity Functions in Cerebral Palsy**

Study Protocol

(Pages 2 – 6)

January 1, 2018

Study Protocol

Study titled 'Investigation of the Effectiveness of Visual Feedback Training on Upper Extremity Functions in Cerebral Palsy was approved by Marmara University Faculty of Medicine Clinical Researches Ethics Committee meeting on 05.01.2018 with approval number: 09.2018.007 (Annex-1).

The legal representatives of the children who participated in the study were informed about the aim, duration and the programs to be applied throughout the study. Volunteer Information Form has been signed and approved in accordance with the standards deemed appropriate by the Clinical Researches Ethics Committee of Marmara University Faculty of Medicine (This form can be seen on Informed Consent Form (ICF) section). The study was conducted in accordance with the Declaration of Helsinki.

Hypothesis of the Study

H0: Addition of the exercises performed with Cogniboard® Light Trainer device to the neurodevelopmental (NDT) based rehabilitation program in patients with cerebral palsy does not contribute positively in improving the efficiency of upper extremity functions.

H1: Addition of the exercises performed with Cogniboard® Light Trainer device to the neurodevelopmental (NDT) based rehabilitation program in patients with cerebral palsy contributes positively to improve the efficiency of upper extremity functions.

Randomization of the Study Groups

Children with Cerebral Palsy who applied to the Dilbade Education and Rehabilitation Center for rehabilitation were invited to participate to the study. Children who volunteered to participate and whom met the criteria for participation were randomized with simple random sampling method and divided into two groups. Individual Neurodevelopmental (NDT) based rehabilitation programs were applied to the participants in both groups. The Cogniboard® Light Trainer education system was added to the rehabilitation program of the Group II (the study group).

Inclusion Criteria

- Volunteered to participate,
- The child and the family have agreed to participate in the study,
- Having a diagnosis of Cerebral Palsy,

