- Children aged between 4 - 18 years,
- Having upper extremity spasticity (0), (1), (1+) according to the modified Ashworth Scale (MAS)
- To be able to cooperate to the exercises

Exclusion Criteria

- Botulinum Toxin (BOTOX) injection applied to the upper extremity within the last 6 months,
- Congenital deformity in upper extremity
- Epileptic attack history,
- Any cardiac or orthopedic problem,
- Visual or hearing impairment

Applied Evaluations

Evaluations are applied twice: before and after the study. All evaluation data are noted to 'Participants Tracking Form' (Annex-2). Spasticity was defined with 'Modified Ashworth Scale'; upper extremity joint range of motion (ROM) with 'goniometer'; grip and pinch strength with 'dynamometer'; hand skills with 'Minnesota Hand Skill Test'; functional abilities with 'Childhood Health Assessment Questionnaire (CHAQ)' and functional level with 'Gross Motor Function Classification System (GMFCS)'

Treatment Program

The participants in our study were all rehabilitated in Dilbade Education and Rehabilitation Center twice a week for 8 weeks, a total of 16 sessions (Duration of one session is 45 minutes).

Group I (Control Group) received individual Neurodevelopmental (NDT) based rehabilitation program.

Group II (Study Group) received individual NDT based rehabilitation program (35 minutes) + Cogniboard® Light Trainer education (10 minutes).

Cogniboard® Light Trainer Education Protocol

Upper limb exercises were applied to the study group with the device which is a training program with visual feedback for 10 minutes in addition to individual 35 minutes neurodevelopmental treatment program. Devices were placed in the mirror so that the participants could see their own reflection. The distances of the participants to the mirror were proportional to their height. For children between 100-149 cm, the distance of the child with the mirror was set as 40 cm and for the children between 149-175 cm, 50 cm. Eight devices were placed in the mirror within the reach of the participant. While the shoulder and wrist were flexed, the shoulder was placed in the lateral distances that the shoulder could reach while the shoulder was in 90°, while the shoulder was in extension and the other devices were placed between these points (Picture 1).

(Picture 1. Application of Cogniboard® Light Trainer Education Device)

Neurodevelopmental Therapy (NDT) Based Upper Extremity Rehabilitation

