In accordance with the needs of the patients for their gross motor functions, the children in both groups were included in the NDT program, which was determined according to the age, sex, mental status and preferences of the individual. NDT program included; rehabilitation of muscle tonus disorders, sensory-perception-motor integrity enhancement, exercises to increase upper extremity functions, stretching and strengthening exercises due to muscular shortness and weakness, exercises to accommodate movements in daily life, and training of activities such as standing up, eating, walking, body care.

**Investigation of the Effectiveness of Visual Feedback
Training on Upper Extremity Functions in Cerebral Palsy**

Statistical Analysis Plan (SAP)

(Pages 7 – 8)

January 1, 2018

Statistical Analysis Plan (SAP)

The statistical program Statistical Package for Social Sciences (SPSS) Version 11.5 (SPSS Inc., Chicago, IL, USA) was used in the data analysis of the study. The p value of $p<0.05$ was considered to be statistically significant in the data analysis. Shapiro-Wilks test was used to investigate the appropriateness of the variables to normal distribution.

In the comparison of the nominal characteristics of the participants in both groups, such as gender, CP type, GMFCS and dominant side, Fisher Precise Chi-Square Test was used.

The initial demographic characteristics such as age, height, weight, body mass index (BMI) of the participants in both groups and the changes before and after the treatment were compared with Independent Samples t-Test and Paired Samples t-Test.

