Annex 2. Participants Tracking Form

Participant's Name - Surname:

Legal Representative Name - Surname:

Phone number:

Age / Gender:

Height:

Weight:

Date of birth:

Type of Cerebral Palsy (CP) (Mark X): **Spastic** **Diskinetic** **Ataxic**

Which side of the arm is effected mostly?

Which side is your dominant side?

How did the problem occur? (Preterm birth, after birth etc. Please explain.)

How many years have you been going to a rehabilitation center?

Did you have any operations? Please write if you did:

Are you using any device? If so, what are they?

Evaluations:

Muscle Tone: (According to the Modified Ashworth Scale 0/1/1+/2/3/4)

Right or Left Arm (Please mark)

Hand Wrist Function:

Elbow Flexion:

Supination:

Do you have any additional medical problems?

Yes / What is it?:

No:

[figure not shown]
Range of Motion:		Before Treatment	After Treatment
Shoulder	Flexion		
	Abduction		
Elbow	Flexion		
Front Arm	Extension		
	Supination		
	Pronation		
Hand Wrist	Flexion		
	Extension		

Muscle Strength	Before Treatment	After Treatment
Grasping		
Tip Pinch		
Lateral Pinch		
Triple Pinch		

Minnesota Hand Skill Test	Before Treatment	After Treatment
Placement with the affected hand (sn)		
Placement bilaterally (sn)		

Gross Motor Functional Classification System (GMFCS)

Level of the participant:

1

CHILDHOOD HEALTH ASSESSMENT QUESTIONNAIRE

2

In this section we are interested in learning how your child's illness affects his/her ability to function in daily life. Please feel free to add any comments on the back of this page. In the following questions, please check the one response which best describes your child's usual activities (averaged over an entire day) **OVER THE PAST WEEK, ONLY NOTE THOSE DIFFICULTIES OR LIMITATIONS WHICH ARE DUE TO ILLNESS**. If most children at your child's age are not expected to do a certain activity, please mark it as "Not Applicable". For example, if your child has difficulty in doing a certain activity or is unable to do it because he/she is too young but not because he/she is RESTRICTED BY ILLNESS, please mark it as "NOT Applicable".

3

	Without ANY Difficulty	With SOME Difficulty	With MUCH Difficulty	UNABLE To do	Not Applicable
--	------------------------------	----------------------------	----------------------------	-----------------	-------------------

4

DRESSING & GROOMING

5 Is your child able to:

6 - Dress, including tying shoelaces and doing buttons?

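### The SAP does not say which t-test decides H1 and adjusts for no baseline; name ANCOVA on each outcome's own baseline as the test of H1 and call the paired tests descriptive

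*Combined protocol and SAP*

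**What the plan says.** Under Hypothesis of the Study, H1 states that adding the device to NDT "contributes positively to improve the efficiency of upper extremity functions". Both groups receive NDT and only Group II receives the device, so the claim concerns a difference between arms.

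Under Randomization of the Study Groups, the children "were randomized with simple random sampling method and divided into two groups". No stratification or other balancing is described.

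Under Applied Evaluations, "Evaluations are applied twice: before and after the study". The list of evaluations includes CHAQ. Annex 2 has before and after columns for 14 continuous measures: 8 ranges of motion, 4 strength measures and 2 Minnesota times.

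The Statistical Analysis Plan handles change in a single sentence. Its subject begins with "The initial demographic characteristics such as age, height, weight, body mass index (BMI) of the participants in both groups" and ends with "the changes before and after the treatment were compared with Independent Samples t-Test and Paired Samples t-Test". No regression, ANCOVA or baseline covariate appears in the SAP text available for review. Some text between that sentence and Annex 2 was not available, so further SAP wording cannot be excluded.

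**The concern.** The sentence can be read in two ways.

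- **Reading A (the ordinary one).** The independent t-test compares change between arms and the paired t-test describes change within each arm.
- **Reading B (respectively).** The independent t-test is for demographics and the paired t-test is for change. This is grammatically possible, since a paired test cannot apply to baseline age or height.

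Under B no outcome is compared between arms. A significant gain in the study arm beside a non-significant one in the control arm could then be taken as support for H1, although that pattern does not compare the arms. Both arms receive active therapy, so gains in both are plausible, and that is when the pattern misleads.

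Under A the overall type I error is sound. But a change-score test fixes the coefficient of the baseline at 1. Once a chance imbalance has occurred, the estimate is shifted: an arm that starts worse appears to improve more, and a study arm that starts better can have a real benefit hidden. The two directions are equally likely.

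**Working it through.** **Inputs.** The available text gives no sample size, SD, effect size or before-after correlation (ρ), so there is no plan figure to reproduce. Assumed: n = 10, 15 or 20 per arm; ρ = 0.5, 0.7 or 0.9; equal SDs of 1; normal data; parallel linear slopes; two-sided 0.05. The SAP gives 0.05 without stating sidedness.

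**1. Reading B: significance in the study arm only.** Let both arms have the same true standardized change d (mean change divided by the SD of change). The chance p that one arm improves significantly comes from the noncentral t with n − 1 df and noncentrality d√n. The arms are independent, so the chance that only the study arm does so is p(1 − p).

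At n = 15 and d = 0.5, p = 0.438 and p(1 − p) = 0.438 × 0.562 = 0.246.

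| d (n = 15) | 0 | 0.3 | 0.5 | 0.7 | 0.8 | 1.0 | 1.2 |
|---|---|---|---|---|---|---|---|
| Study arm only | 2.4% | 15% | 25% | 21%* | 15% | 4.8% | 0.9% |

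*20.5% before rounding. At d = 0.5 the figure is 21% with 10 per arm and 25% with 20. A two-sided between-arm test errs in the device's favour 2.5% of the time.

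**2. Reading A: precision.** Per child, the variance is 2(1 − ρ) for change and 1 − ρ² for ANCOVA, a ratio of (1 + ρ)/2. Allowing for estimation of the slope, with N = 2n:

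expected ratio = (1 + ρ)/2 × (N − 3)/(N − 4).

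At n = 15 and ρ = 0.5: 0.75 × 27/26 = 0.78.

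| n per arm | ρ = 0.5 | ρ = 0.7 | ρ = 0.9 | Break-even ρ = 2(N − 4)/(N − 3) − 1 |
|---|---|---|---|---|
| 10 | 0.80 | 0.90 | 1.01 | 0.88 |
| 15 | 0.78 | 0.88 | 0.99 | 0.93 |
| 20 | 0.77 | 0.87 | 0.98 | 0.95 |

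Above the break-even ρ the change score is slightly more precise. Simulated power at 15 per arm for a 0.5 SD effect, change against ANCOVA: 26% v 32%, 40% v 44%, and about 84% for both. Both methods keep about 5% error overall.

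**3. Reading A: after an imbalance has occurred.** The change-score estimate is shifted by (1 − ρ) × imbalance. For 0.5 SD that is 0.5 × 0.5 = 0.25, 0.3 × 0.5 = 0.15 and 0.1 × 0.5 = 0.05 SD. Simulated rates at 15 per arm:

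| Situation | Change, ρ = 0.5 / 0.7 / 0.9 | ANCOVA |
|---|---|---|
| No effect, study arm 0.5 SD worse: false positives | 7.0 / 6.4 / 5.5% | about 5% |
| No effect, 0.25 SD imbalance: false positives | 3.6 / 4.2 / 4.7% | about 5% |
| True 0.5 SD effect, study arm 0.5 SD better: power | 7 / 21 / 77% | 31 / 43 / 83% |
| True 0.5 SD effect, study arm 0.5 SD worse: power | 51 / 61 / 91% | 31 / 43 / 83% |

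In the first row almost all change-score errors favour the study arm (6.9, 6.0 and 4.5 points). With 10 per arm that row is 5.4 / 5.3 / 5.0%, and with 20 per arm 8.8 / 7.4 / 5.8%.

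**4. How often such an imbalance arises.** For one outcome, P(|imbalance| > 0.5 SD) = 2(1 − Φ(0.5/√(2/n))) = 26%, 17% and 11% at 10, 15 and 20 per arm. For at least one of the 14 outcomes at 15 per arm it is 93%, 79%, 62% or 39% if the baselines correlate 0, 0.5, 0.7 or 0.9.

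**The case against.** Two points of unequal weight are joined here. The unclear assignment of tests is a drafting gap that one sentence could close without ANCOVA. The missing covariate is mainly a matter of efficiency: under the ordinary reading the t-test on change is valid, and the power gain at 15 per arm is 6 points, 4 points and nil. Eligibility is wide ("Children aged between 4 - 18 years"), which may raise ρ and shrink the gain. The largest error figures need Reading B and an inference rule that the plan states nowhere, and they fade once d exceeds about 0.8. An imbalance helps the change-score test as often as it hurts it, and a count of imbalances is not a count of wrong conclusions. Finally, 14 ANCOVAs do not make one test of H1: at 0.05 each, the family-wise error would be 1 − 0.95^14 = 51% if the outcomes were independent.

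All of this is correct as arithmetic and limits the size of the point. It does not remove it. The plan still leaves the deciding test open. The two directions of imbalance are the same conditional error with opposite signs, and ANCOVA removes it at almost no cost. The lack of a primary outcome or multiplicity rule in the available text is a separate gap that exists equally under the planned t-tests.

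**Conclusion.** The concern holds for the SAP text available for review. The plan does not identify the between-arm test that decides H1, does not restrict the paired tests to description, and makes no use of baseline values it already collects.

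The ambiguity is the more serious part: under Reading B a false one-arm pattern can occur in up to about a quarter of trials. The missing covariate is a moderate loss, not a type I error fault: ANCOVA cuts variance by roughly 10% to 23% at ρ of 0.5 to 0.7, by almost nothing at 0.9, and by less than nothing at ρ = 0.9 with 10 per arm. The conditional shift raises false positives only for larger imbalances, of the order of 0.5 SD. Every size quoted rests on assumed n, ρ and effect, and on normal data with parallel slopes.

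**What to change.** For each continuous outcome with a before and an after value (range of motion, grip and pinch strength, Minnesota times, and the CHAQ score if analysed as continuous), name as the test of H1 an ANCOVA of the after-treatment value on group, with that outcome's before-treatment value as covariate. Report the adjusted between-arm difference with its 95% CI. State that paired t-tests describe change within a group and do not decide H1. Check normality on the model residuals, with a pre-stated alternative.

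This removes the linear error from that outcome's own baseline imbalance only. It does not address imbalance in age, CP type or GMFCS. It does not cover the ordinal MAS and GMFCS, and it does not replace a primary outcome or multiplicity rule.

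The cost is SAP wording and one regression per continuous outcome, with no extra data. Each model spends one degree of freedom. The worst loss among the cases shown is about 1% more variance, at ρ = 0.9 with 10 per arm.

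### Does the unclear role of the Modified Ashworth Scale, with no number given for grade 1+, call for a change to the SAP?

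*Combined protocol and SAP*

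**What the plan says.** Under Applied Evaluations the protocol states "Evaluations are applied twice: before and after the study" and "All evaluation data are noted to 'Participants Tracking Form' (Annex-2"). The list that follows opens with "Spasticity was defined with 'Modified Ashworth Scale" and closes with "functional abilities with 'Childhood Health Assessment Questionnaire (CHAQ)' and functional level with 'Gross Motor Function Classification System (GMFCS"). MAS is also an inclusion criterion: "Having upper extremity spasticity (0), (1), (1+) according to the modified Ashworth Scale (MAS").

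In Annex 2 the MAS block has the arm to be marked and one blank each for hand wrist, elbow flexion and supination. GMFCS has one blank and the CHAQ is printed once. Only range of motion, muscle strength and the Minnesota test have separate columns for before and after treatment.

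The SAP sends nominal characteristics, GMFCS among them, to Fisher's exact test. For age, height, weight and BMI, and for pre-post differences in general, it says that "the changes before and after the treatment were compared with Independent Samples t-Test and Paired Samples t-Test". It does not name MAS. The alternative hypothesis is that adding the device "contributes positively to improve the efficiency of upper extremity functions".

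**The concern.** Read literally, the protocol has MAS measured twice, and the only before-after method in the visible SAP is the t-test. MAS is ordinal and one of its three eligible grades, 1+, is not a number. A t-test cannot be run on 0, 1 and 1+ until a code is chosen, and the documents give none. If the code were picked after the data were seen, the between-group verdict on spasticity could turn on that choice.

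The therapy description gives the idea some support, since the "NDT program included; rehabilitation of muscle tonus disorders": muscle tone is something the treatment works on, so a spasticity result might be expected. A reader who finds one MAS entry on the form cannot tell whether such a result is planned.

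**Working it through.** **1. Reading the texts side by side.** The sentence about two evaluations covers MAS, GMFCS and CHAQ alike, and all three have a single entry on the form. The missing columns therefore do not show that MAS was taken only once; a second copy of the form could have been used. They do show that the sentence cannot, by itself, make an instrument an outcome, because GMFCS falls under it and the SAP treats GMFCS as a group characteristic. MAS has an eligibility role, the hypotheses concern function, and no visible sentence calls MAS an outcome. The tone wording describes therapy given to both groups, not an endpoint. The descriptive reading is the better supported one. Under it, the baseline grades 0, 1 and 1+ can be compared as categories with Fisher's exact test, as for GMFCS, and no code is needed.

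**2. What a code would do if MAS change were tested.** The documents have no figure to reproduce. The visible text gives no sample size, variance or effect size, so every input here is assumed: 15 children per arm, 5 at each of grades 0, 1 and 1+, and improvement by one level only. In the control arm 1 of 5 improves from grade 1 and 1 of 5 from 1+. In the study arm 3 of 5 and 4 of 5 do. Tests are two-sided.

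Let c be the code for 1+. A step from 1 to 0 is worth 1, and a step from 1+ to 1 is worth c − 1.

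- Mean change, control: −[1 + (c − 1)]/15 = −c/15
- Mean change, study: −[3 + 4(c − 1)]/15 = −(4c − 1)/15
- Difference, study minus control: −(3c − 1)/15
- t = difference / √(s²·2/15), where s² is the pooled variance, with 28 degrees of freedom

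At c = 1.5 the difference is −0.233, s² = (0.0786 + 0.1667)/2 = 0.1226, t = −1.82 and p = 0.079. At c = 2 the difference is −0.333, s² = (0.1238 + 0.2667)/2 = 0.1952, t = −2.07 and p = 0.048.

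| Code for 1+ | Between-group p | Paired p, study | Paired p, control |
|---|---|---|---|
| 1.25 | 0.145 | 0.020 | 0.24 |
| 1.5 | 0.079 | 0.007 | 0.19 |
| 1.75 | 0.055 | 0.004 | 0.17 |
| 2 | 0.048 | 0.004 | 0.16 |

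The between-group result crosses 0.05 at about c = 1.89. The paired verdicts do not change.

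**3. The proposed replacement on the same data.** The van Elteren test on post-treatment grade, stratified by baseline grade, needs only the order of the grades. Children at baseline 0 contribute nothing. The other two strata have 10 children each and so carry equal weight, and the statistic reduces to the number of study-arm improvers.

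- Observed: 3 + 4 = 7
- Expected: 5·4/10 + 5·5/10 = 4.5
- Variance: 5·5·4·6/(100·9) + 5·5·5·5/(100·9) = 0.667 + 0.694 = 1.361
- z = 2.5/√1.361 = 2.14, p = 0.032

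The exact stratified permutation p-value, from the product of the two hypergeometric distributions, is 0.077. The verdict now turns on the choice between approximate and exact calculation.

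**4. How often the code matters.** These are simulated trials with equal thirds at each baseline grade. The entries are the share in which coding 1+ as 1.5 or as 2 gives different between-group verdicts.

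| Improvement, control vs study | 10 per arm | 15 per arm | 30 per arm |
|---|---|---|---|
| 30% vs 30% (no effect) | 0.8% | 2.0% | 3.3% |
| 20% vs 40% | 1.5% | 4.1% | 8.4% |
| 20% vs 55% | 4.5% | 9.5% | 11.3% |

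With no effect, the t-test rejected in 2.1% to 5.4% of trials across the codes.

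**5. Power.** At 20% vs 55% and 30 per arm, van Elteren had power 0.62, against 0.42, 0.52 and 0.56 for the t-test at codes 1.25, 1.5 and 2. When only children starting at grade 1 benefit (20% vs 70%, 30 per arm), it had 0.42 against 0.46, 0.44 and 0.35. It is often better, but not always.

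**The case for a change.** The best case for a change is that the mismatch is real, the repair is short, and the code can reverse even the direction of a result. Take 20 children per group, with 12 in one group moving from 1+ to 1, 4 in the other moving from 1 to 0, and no other change. The difference in mean change is −12(c − 1)/20 + 4/20. That is +0.05 (p = 0.61) at c = 1.25 and −0.40 (p = 0.009) at c = 2. One sentence on the role of MAS would remove the doubt.

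The arithmetic stands, and so does the mismatch between Applied Evaluations and Annex 2. It would be reasonable to ask the sponsor which evaluations were repeated and where the second values are kept. That question matters more for the CHAQ, which lies closer to the hypothesis. But the case for altering the analysis needs a MAS change analysis that no visible text plans. The reversal needs all improvers in one group to start at 1+ and all those in the other to start at 1, which randomisation makes unlikely. Some text after the visible SAP paragraphs was removed before review, so a rank test or a coding rule there cannot be ruled out. The replacement also has costs: it gives no mean difference, a baseline stratum with children from only one arm is lost, and it is unconfirmed that SPSS 11.5 runs it.

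**Conclusion.** No change to the plan follows. The form mismatch is clerical and general, and is not a statement about how MAS is analysed. The missing number for 1+ is a gap only if MAS change is tested. The visible SAP does not say that it is, and an analyst who follows the better-supported reading will describe MAS by grade and need no code. If a sponsor did analyse MAS change, one code fixed beforehand would be adequate: it does not inflate type I error, and the choice between 1.5 and 2 alters the verdict in 0.8% to 11.3% of simulated trials. Choosing van Elteren instead is a trade-off without a clear gain, as the 0.032 and 0.077 on the same data show.

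All of these sizes rest on assumed sample sizes, baseline mixes and improvement rates. The conclusion itself rests on the documents: MAS is an eligibility criterion, the visible SAP does not name it, and the hypotheses concern function. It would need to be looked at again if the removed text named MAS change as an outcome and gave no method for it.
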